## **8. RESEARCH METHODS**

### **8.1. Study design**

The study will be a retrospective cohort analysis using the Premier Hospital database. The overall study period will be from January 1, 2012 through September 30, 2017, to allow for a 1 month follow up period for observation of readmissions and a 1-year baseline observation period. Adult patients (age  $\geq 18$  years) hospitalized for NVAF, based on a primary or secondary discharge diagnosis code indicating NVAF, will be identified from the Premier Hospital database between January 1, 2013 and June 30, 2017. Patients who received apixaban, dabigatran, rivaroxaban, or warfarin during any time of the hospitalization (from admission to discharge) will be identified and grouped into study cohorts based on the OAC initiated. The first of such NVAF hospitalizations will be defined as the index hospitalization. Patients with more than one type of OAC drug usage during the index hospitalizations will be excluded so that patients can be exclusively assigned into each OAC patient cohorts. Demographic, patient clinical characteristics, hospital characteristics, and key anticoagulant treatment-related information will be measured during the index hospitalization of NVAF patients. Other clinical characteristics (e.g. prior bleeding) of NVAF patients will be measured during a 12-month baseline period. The proportions of patients treated with apixaban, dabigatran, rivaroxaban, and warfarin that have MB-related, all-cause, and stroke-related readmissions that occur within 1 month of discharge of their initial hospitalization for NVAF will be evaluated. Hospital LOS and associated costs of MB-related, all-cause, and stroke-related readmissions will be determined and compared between the other OAC cohorts and the apixaban cohort.

Note: We anticipate that the sample size of patients treated with edoxaban is low and thus we have not included patients treated with edoxaban in this study evaluation. This is consistent with previous alliance NVAF studies.

**Figure 1. Study Time Periods** (for illustration purposes, may not be proportional)

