## 8.2. Setting

Adult patients (age  $\geq 18$  years) hospitalized for NVAf, based on a primary or secondary discharge diagnosis code indicating NVAf, will be identified from the Premier Hospital database between January 1, 2013 and June 30, 2017. Patients who received apixaban, dabigatran, rivaroxaban, or warfarin during any time of the hospitalization (from admission to discharge) will be identified and grouped into study cohorts based on the OAC initiated. The first of such NVAf hospitalizations will be defined as the index hospitalization, with the corresponding hospital discharge date as the index date.

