- Had medical claims indicating a hip or knee replacement surgery during the index hospitalizations or within a 6-week period prior to the index date
  1. ICD-9 diagnosis codes V43.64 and V43.65
  2. ICD-10 diagnosis codes Z96.64x and Z96.65x
  3. ICD-9 procedure codes 81.40, 81.51, 81.52, 81.53, 81.54, and 81.55
  4. ICD-10 procedure codes 0SQ9x, 0SQBx, 0SR9019-0SR904Z, 0SR907Z, 0SR90Jz, 0SR90KZ, 0SRAx, 0SRB019-0SRB04Z, 0SRB07Z, 0SRB0Jx, 0SRB0KZ, 0SRC07Z, 0SRC0Jx, 0SRC0KZ, 0SRC0Lx, 0SRD07Z, 0SRD0Jx, 0SRD0KZ, 0SRD0Lx, 0SREx, 0SRRx-0SRWx, 0SW90JZ, 0SW93JZ, 0SW94JZ, 0SWA0JZ, 0SWA3JZ, 0SWA4JZ, 0SWB0JZ, 0SWB3JZ, 0SWB4JZ, 0SWC0JC, 0SWC0JZ, 0SWC3JC, 0SWC3JZ, 0SWC4JC, 0SWC4JZ, 0SWD0JC, 0SWD0JZ, 0SWD3JC, 0SWD3JZ, 0SWD4JC, 0SWD4JZ, 0SWE0JZ, 0SWE3JZ, 0SWE4JZ, 0SWR0JZ, 0SWR3JZ, 0SWR4JZ, 0SWS0JZ, 0SWS3JZ, 0SWS4JZ, 0SWT0JZ, 0SWT3JZ, 0SWT4JZ, 0SWU0JZ, 0SWU3JZ, 0SWU4JZ, 0SWV0JZ, 0SWV3JZ, 0SWV4JZ, 0SWW0JZ, 0SWW3JZ, and 0SWW4JZ.
- Had medical claims indicating pregnancy at any time during the study period
  1. ICD-9 diagnosis codes 630-679, V22, V23, V24, V27, V28, V61.6, V61.7, 792.3, and 796.5
  2. ICD-10 diagnosis codes A34, O00.00-O9A.53, Z33.1-Z37.9, Z39.x, and Z64.0
  3. ICD-9 procedure codes 72-75.9
  4. ICD-10 procedure codes 0DQPx-0DQQ8ZZ, 0DQRx, 0JCBx, 0Q82x, 0Q83x, 0TQBx, 0TQDx, 0U7C7ZZ, 0UCG0ZZ, 0UCG3ZZ, 0UCG4ZZ, 0UCM0ZZ, 0UJD7ZZ, 0UQ9x, 0UQCx, 0UQGx, 0UQMx, 0US90ZZ, 0US94ZZ, 0US9XZZ, 0W3Rx, 0W8NXZZ, 0WQNXZZ, 109x, 10A00ZZ, 10A03ZZ, 10A04ZZ, 10A07Z6, 10A07ZX, 10A07ZZ, 10A08ZZ, 10D0x, 10D1xZZ, 10Ex-10S0x, 10T20ZZ-10T24ZZ, 10Yx, 2Y44X5Z, 3027x, 3E030VJ, 3E033VJ, 3E040VJ, 3E043VJ, 3E050VJ, 3E053VJ, 3E060VJ, 3E063VJ, 3E0DXGC, 3E0E305-3E0E3TZ, 3E0E705, 3E0E729-3E0E7TZ, 3E0E805, 3E0E829-3E0E8TZ, 3E0P7GC, 4A0Hx, 4A0Jx, 4A1Hx, and 4A1Jx
- Received edoxaban during the index hospitalization or within 12 months prior to the index date
- Received multiple types of OACs during the index hospitalization

- Patients who died during the index hospitalizations

All the ICD-10 codes corresponding to the ICD-9 codes listed above will also be used to identify the conditions and procedures in the inclusion and exclusion criteria.

These inclusion and exclusion criteria are aligned with the Eliquis Harmonized Retrospective Study Protocol and are consistent with other previous apixaban retrospective database studies of patients with NVAf.

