**Table 2. Outcome Measurements: Readmissions and Associated LOS and Cost/Charges**

Variable	Role	Operational definition
MB-related Readmission	Outcome	
Defined as readmissions with a bleeding diagnosis at the first position of the hospital discharge diagnosis codes.
 
Number and percentage of patients with MB-related readmissions within 1 or 3 months of initial NVAF hospitalization in study cohorts will be reported. Associated LOS and cost for MB-related readmissions will be determined. Likelihood of first MB-related readmission was assessed for each OAC cohort vs. the apixaban cohort. LOS and hospital cost per patient for cohorts will be estimated and compared by multivariable regression analysis. Measurements for 3-month readmissions will be evaluated using descriptive statistics as an exploratory analysis.

All-cause Readmission	Outcome	
Number and percentage of patients with all-cause readmissions within 1 or 3 months of initial NVAF hospitalization in study cohorts will be reported. Associated LOS and cost for all-cause readmissions will be determined. Likelihood of first all-cause readmission was assessed for each OAC cohort vs. the apixaban cohort. LOS and hospital cost per patient for cohorts will be estimated and compared by multivariable regression analysis. Measurements for 3-month readmissions will be evaluated using descriptive statistics as an exploratory analysis.

Stroke-related Readmission	Outcome	
Defined as readmissions with a stroke diagnosis at the first position of the hospital discharge diagnosis codes. Cases will be excluded if traumatic brain injury (ICD-9: 800-804, 850-854) was present during hospitalization.
 
Number and percentage of patients with stroke-related readmissions within 1 or 3 months of initial NVAF hospitalization in study cohorts will be reported. Associated LOS and cost for stroke-related readmissions will be determined. Measurements for stroke-related readmissions will be evaluated using descriptive statistics as an exploratory analysis.

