### 8.5. Study size

The preliminary data evaluation of the Premier database indicated that there are at least 30,000 patients for each of OAC cohort during the study period described for this study. With a two-sided test, an alpha-level of 0.05, and a 1:1 ratio of the comparison cohorts, and the assumed one-month MB-related readmission rate of 1.4%, and the assumed MB-related readmission rate difference of 0.5% between cohorts treated with other OACs vs. apixaban, we have estimated the following power calculation.

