### 8.7. Data analysis

Means  $\pm$  standard deviations, and medians will be provided for continuous variables. Numbers and percentages will be provided for dichotomous and polychotomous variables. Bivariate comparisons of baseline patient and hospital characteristics and readmission measurements will be provided, with appropriate tests (e.g., ANOVA test, chi-square test) used based on the distribution of the measure. A propensity score matching (PSM) 1:1 technique will be used to control for confounders when comparing each of the OAC cohorts vs. the apixaban cohort. A logistic regression analysis will be carried out on the matched patient cohorts to further evaluate the potential impact of treatment with the different OACs vs. treatment with apixaban on 1-month MB-related and all-cause readmissions. Only the index drug will be the covariate, since other patient characteristics are expected to be similar already after the PSM. Since the patient sample size attribution in the PSM process is not known, if the population sizes are not sufficient after the PSM attrition, a multivariable logistic regression analysis will be carried out to assess the potential impact of treatment with the different OACs compared to treatment with apixaban on 1-month MB-related and all-

cause readmissions, separately. The independent covariates in the regression analyses will include key patient demographics and hospital characteristics. The final list of such covariates will be determined with inputs from the Pfizer team. Additionally, we will carry out a two-part model analysis and a generalized linear model with log transformation and gamma distribution to examine the impact of treatment with the 3 different OACs vs. apixaban on MB-related and all-cause hospital readmission costs. Measurements related to exploratory objectives will be analyzed using descriptive statistics. All data analysis will be executed using statistical software SAS version 9.4.

Detailed methodology for summary and statistical analyses of data collected in this study will be documented in a Statistical Analysis Plan (SAP), which will be dated, filed and maintained by the sponsor. The SAP may modify the plans outlined in the protocol; any major modifications of primary endpoint definitions or their analyses would be reflected in a protocol amendment.

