### **8.9. Strengths and limitations of the research methods**

A key strength is that retrospective analyses provide a better understanding of the study population in real-world clinical practice as compared to the controlled conditions of a clinical trial. Retrospective database studies allow observation of patients who are often under-represented in clinical trials, such as those with comorbidities and the elderly.

Patient data in the Premier Hospital database are only representative of hospital costs and exclude outpatient healthcare utilization and costs not received in a hospital. While the Premier Hospital database contains information from a large number of hospitals across the U.S., it is possible that it may not be representative of the entire U.S. population of NVAF patients. Additionally, patient treatment information and history in the outpatient settings are not available in the Premier Hospital database. Also, hospital readmissions are only captured when patients are readmitted to the same Premier database hospitals. Lastly, billing and coding errors and missing data could potentially occur on database records.

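### Index stays that end in transfer to another acute hospital are kept as at risk from the transfer date, which mainly distorts the all-cause readmission, length-of-stay and cost outcomes

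*Protocol*

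**What the plan says.** Protocol section 8.2 defines the index hospitalization as the first qualifying stay, "with the corresponding hospital discharge date as the index date". Section 8.1 adds that "readmissions that occur within 1 month of discharge of their initial hospitalization for NVAF will be evaluated".

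Section 8.2.2 excludes many clinical conditions and some drug exposures. Only one criterion turns on how the index stay ended: "Patients who died during the index hospitalizations".

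Table 2 defines the outcome as a proportion of the cohort: "Number and percentage of patients with MB-related readmissions within 1 or 3 months of initial NVAF hospitalization in study cohorts will be reported". It has no rule that separates a transfer from a readmission. Table 1 lists no discharge disposition.

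On capture, section 8.9 says that "hospital readmissions are only captured when patients are readmitted to the same Premier database hospitals". It does not mention transfers. The outcome model in section 8.7 adds no adjustment in the matched cohorts: "Only the index drug will be the covariate, since other patient characteristics are expected to be similar already after the PSM".

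**The concern.** A patient who leaves the index hospital for another acute hospital has not ended the acute episode. On the index date that patient is still an inpatient, so readmission is not yet possible in the ordinary sense. Two errors follow from the plan as written:

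- **The patient does not come back to the index hospital.** The rest of the episode and any later admission elsewhere are unseen, and the patient counts as event-free.
- **The patient is sent straight back.** The second half of the same episode counts as an all-cause readmission and brings its length of stay and cost into the secondary outcomes.

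If section 8.9 means any hospital in the database rather than the index hospital alone, the receiving stay may itself be recorded as an admission on the index date. Nothing in Table 2 stops it from counting.

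At stake are the reported frequencies, which the primary research question asks for, and the all-cause, length-of-stay and cost comparisons.

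**Working it through.** **Inputs from the protocol.** MB rate 1.4%, assumed difference 0.5 points, two-sided alpha 0.05, 1:1 ratio and at least 30,000 patients per cohort (section 8.5); all-cause 1-month rate 18%, from a cited study of 6,439 patients (section 6).

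**Assumptions (no figures in the documents).** A share *f* of 2–6% of index stays whose readmission cannot be seen; a difference in *f* of 1–3 points between drugs after matching; all such patients scored as non-events. The 30,000 is treated as the matched size, although section 8.5 does not say that it survives matching. Smaller matched cohorts would raise the standard errors.

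**Step 1: the plan's own figure.** The pooled two-proportion formula at 1.4% vs 0.9% and 80% power gives 7,137 per arm, or 14,274 in total, which is the Table 3 entry. All six rows reproduce as two-arm totals. Table 3 is not in dispute; it shows how much sample there is to spare.

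**Step 2: reported frequencies.** Observed rate = true rate × (1 − *f*).

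- All-cause: 18% × 0.98 = 17.6%; 18% × 0.94 = 16.9%.
- MB: 1.4% × 0.98 = 1.37%; 1.4% × 0.94 = 1.32%.

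**Step 3: false difference between cohorts with equal true rates.** False difference *b* = rate × gap in *f*. Standard error (SE) = √(2p(1−p)/n).

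- All-cause SE: √(2 × 0.18 × 0.82 / 30,000) = 0.31 points.
- MB SE: √(2 × 0.014 × 0.986 / 30,000) = 0.096 points.
- False rejection at two-sided 5%: Φ(b/SE − 1.96) + Φ(−b/SE − 1.96).

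| Gap in *f* | All-cause *b* | *b*/SE | False rejection | MB *b* | *b*/SE | False rejection |
|---|---|---|---|---|---|---|
| 1 point | 0.18 | 0.57 | about 9% | 0.014 | 0.15 | about 5% |
| 3 points | 0.54 | 1.72 | about 41% | 0.042 | 0.44 | about 7% |

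The MB error is 0.014/0.5 = 3% to 0.042/0.5 = 8% of the assumed difference. With non-capture of 2% vs 5% the spurious MB odds ratio is 1.03.

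**Step 4: returns work the other way.** Suppose 3% are transferred and 10% of those return directly and are counted.

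- False readmissions added: 3% × 10% = 0.30 points.
- True readmissions lost: 3% × 18% = 0.54 points.
- Net: 0.24 points too low. A 1-point gap in transfer share then gives 1% × (18 − 10) = 0.08 points, about a quarter of the SE.

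The sign reverses if more than 18% of transferred patients return and are counted. For all-cause readmission, neither direction nor size can be fixed in advance.

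**Step 5: equal non-capture.** If *f* is the same in both cohorts, even 10% leaves power at 30,000 per cohort above 99.9% for 1.4% vs 0.9%. The issue is misclassification, not power.

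**The case against.** The case on the other side is substantial.

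- **The primary comparison is hardly touched.** This stands. A reader might infer from the primary question that the MB comparison is seriously biased. Step 3 does not support that, and the earlier study in section 6 reported odds of 1.2- and 1.4-fold. A bleed during continued care elsewhere is also not automatically a missed endpoint, because Table 2 requires a readmission with bleeding coded first.
- **Table 1 already holds correlates of transfer.** Bed size, urban/rural and teaching status, region, Charlson index, heart failure and index stroke are listed for confounding control. This stands in part: they may narrow a difference between drugs, but they do not correct the frequencies or stop a return from being counted.
- **The figures are assumed and the all-cause range stacks unfavourable assumptions.** This stands. Step 4 shows how far netting can shrink it.
- **The limitation is disclosed and the rest is for the SAP.** This does not carry. Section 8.9 states the capture limit without handling transfers, and eligibility and outcome definitions are fixed in section 8.2.2 and Table 2.
- **Disposition is decided after in-hospital exposure.** This stands against matching on it, since the drug may affect it, for example through transfer after an in-stay bleed. Excluding transfers also selects on a post-exposure event, as the death exclusion already does. That is a reason to show disposition by cohort.

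A reader might also infer that hospice discharges must be excluded as an error. The documents do not support that. These patients have been discharged alive and can in principle be readmitted, so keeping them is a choice of target population.

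**Conclusion.** The point holds for acute transfers. As written, the plan counts patients who are still in acute care elsewhere as at risk, mostly records them as not readmitted, and counts a direct return as a new all-cause readmission with its length of stay and cost.

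The effect falls mainly on the all-cause, length-of-stay and cost outcomes and on the reported frequencies. Under the assumed shares, frequencies are understated by a relative 2–6%, before any counted returns. The false all-cause difference could reach 0.18–0.54 points, less once returns are netted, and the false MB difference 0.014–0.042 points. Bias in any comparison requires transfer to differ by drug after matching, and the documents show neither that it does nor in which direction. The change is worth making because it is cheap and a larger sample does not remove the misclassification.

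**What to change.** 1. **Section 8.2.2:** next to the death criterion, exclude index stays whose discharge status is transfer to another acute care hospital.
2. **Table 2:** state that a direct transfer-in continuing the index episode is not a readmission and contributes no readmission length of stay or cost.
3. **Descriptive table:** report discharge disposition by cohort, so that readers can see whether it differs by drug. Do not add it to the propensity score.
4. **Sensitivity analysis:** repeat the readmission comparisons with hospice discharges excluded.

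**Cost.** Protocol wording and matching SAP text. The death exclusion already implies a discharge-status field. Even losing the full assumed 6% would leave 30,000 × 0.94 = 28,200 per cohort before matching, against the 11,815 per arm (half of 23,630) that Table 3 implies for 95% power. Results would no longer describe transferred patients, and the report should say so.

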### 8.2.3. Cohorts

After applying the inclusion and exclusion criteria, eligible patients will be assigned to the following cohorts based on the OAC treatment received during index hospitalizations.

1. **Apixaban Cohort:** NVAf patients who initiated apixaban during hospitalization
2. **Dabigatran Cohort:** NVAf patients who initiated dabigatran during hospitalization
3. **Rivaroxaban Cohort:** NVAf patients who initiated rivaroxaban during hospitalization
4. **Warfarin Cohort:** NVAf patients who initiated warfarin during hospitalization

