### 8.2.1. Inclusion criteria

Patients must meet all the following inclusion criteria to be eligible for inclusion in the study:

- Have a hospital discharge ICD-9-CM code of 427.31 or 427.32 (and corresponding ICD-10 codes) indicating a primary or secondary diagnosis of AF identified from the Premier Hospital database between January 1, 2013 and September 30, 2017.
- Received any of the OACs, apixaban, dabigatran, rivaroxaban, or warfarin during any time of the hospitalization from admission to discharge
- Have an age  $\geq 18$  years as of the initial hospitalization with an AF diagnosis

Note: All the medical codings, e.g. ICD-9, ICD-10, CPT/HCPCS codes used in the patient selection criteria are consistent with the Eliquis Harmonized Retrospective Study Protocol.

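### Cohorts are labelled by the anticoagulant initiated, but the rule is any in-hospital receipt, so every cohort mixes new and continuing users in unknown and possibly unequal shares

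*Protocol*

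**What the plan says.** Section 8.2 says patients are "grouped into study cohorts based on the OAC initiated", and Section 8.1 and the abstract say the same. Section 8.2.3 then lists the cohorts, for example "NVAf patients who initiated apixaban during hospitalization" and "NVAf patients who initiated warfarin during hospitalization". The word *initiated* is not defined anywhere.

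The operative rules are different. The inclusion criterion in Section 8.2.1 is "Received any of the OACs, apixaban, dabigatran, rivaroxaban, or warfarin during any time of the hospitalization from admission to discharge". The lead-in to Section 8.2.3 itself says patients are "assigned to the following cohorts based on the OAC treatment received during index hospitalizations".

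On earlier drug use, Section 8.2.2 has one look-back, for a drug outside the comparison: "Received edoxaban during the index hospitalization or within 12 months prior to the index date". For the four study drugs the only exclusion is "Received multiple types of OACs during the index hospitalization". Table 1 has two anticoagulant variables, DOAC dose strength and other anticoagulants, and both describe the index stay. Section 8.7 puts only the index drug in the regression after matching.

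Section 8.9 concedes that "patient treatment information and history in the outpatient settings are not available in the Premier Hospital database", but does not connect this to the cohort definition.

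**The concern.** A patient on long-term warfarin, admitted for another reason with a secondary atrial fibrillation code, meets every stated inclusion criterion and would be described as having initiated warfarin in hospital. The same is true of a long-term apixaban user.

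Two things follow. First, results would be labelled as applying to initiators when nothing requires the patients to be initiators. Second, if new and continuing users differ in 1-month bleeding risk, and their shares differ between drugs, the primary odds ratios combine a drug effect with a user-status effect. Nothing that the protocol lists as a confounder measures user status directly, so the planned matching has no specific means of balancing it.

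**Working it through.** **Text comparison.**

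| Place | Exposure wording |
|---|---|
| Abstract, 8.1, 8.2 | grouped by drug *initiated* |
| 8.2.1 | drug *received* at any time in the stay |
| 8.2.3, lead-in | drug *received* |
| 8.2.3, cohort list | drug *initiated* |
| 8.2.2 | no exclusion for earlier use of the four study drugs |
| Table 1 | no variable for earlier use of an oral anticoagulant |

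Only the *received* wording can be applied as a rule. The *initiated* wording has no criterion behind it.

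**Possible size.** The plan gives no figure on user status, so there is nothing to reproduce and all inputs here are assumptions. Let pc and pa be the shares of continuing users in the comparator and apixaban cohorts, and RR the 1-month bleeding risk of new users relative to continuing users. With no true drug effect:

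apparent ratio = (pc + (1 − pc)·RR) / (pa + (1 − pa)·RR)

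| RR | pc 0.6, pa 0.5 | pc 0.7, pa 0.4 |
|---|---|---|
| 1.25 | 1.100/1.125 = 0.978 | 1.075/1.150 = 0.935 |
| 1.5 | 1.20/1.25 = 0.960 | 1.15/1.30 = 0.885 |
| 2 | 1.40/1.50 = 0.933 | 1.30/1.60 = 0.812 |

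At event rates near 1.4% the odds ratio is almost the same as this risk ratio.

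**Limits of the range.**
- If pc = pa, numerator and denominator are equal and the ratio is 1.0 for any RR.
- If continuing users bleed more, the sign turns. With RR = 1/2, pc = 0.7 and pa = 0.4, the ratio is (0.7 + 0.15)/(0.4 + 0.30) = 0.85/0.70 = 1.21.

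**Why sample size does not help.** Take the 1.4% of Section 8.5 as the apixaban rate (an assumption), shares of 60% vs 40%, and the full 30,000 patients per cohort that Section 8.5 mentions.
- RR 1.25: comparator rate 1.4% × 1.10/1.15 = 1.339%, a spurious difference of −0.061 points.
- RR 2: comparator rate 1.4% × 1.40/1.60 = 1.225%, a spurious difference of −0.175 points.

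A two-sided 5% test of two proportions would then reject a true null in about 9% and 47% of studies. Fewer patients after matching would lower these figures. The bias itself would not shrink.

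**What a hospital look-back can see.** The index stay is the first qualifying stay from January 1, 2013. An earlier stay in that window with an atrial fibrillation code and a study drug would itself be the index. A 12-month look-back therefore adds mainly (a) stays in 2012 for patients indexed in 2013 and (b) stays with an anticoagulant but no atrial fibrillation code. The exclusions for venous thromboembolism within 12 months and joint replacement within 6 weeks make group (b) smaller still.

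**The case against.** The strongest reply is that no objective speaks of initiators: the research question and all objectives refer to patients treated with each drug, so the label is loose but the question is not. That stands, and it is why relabelling is the right repair. It does not remove the possible imbalance in user status, which affects a comparison of treated patients just as much.

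Three stronger readings are tempting and are not supported.

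- A reader might infer that established warfarin users are being compared with new apixaban users. The same receipt rule governs all four cohorts, so apixaban can also contain continuing users. A higher continuing share on warfarin is plausible, but the documents do not quantify it.
- A reader might infer from the edoxaban look-back that one for the study drugs was simply overlooked. Edoxaban receipt does not define an index stay, so it needs its own clause. The first-stay rule already removes most visible earlier in-hospital use for atrial fibrillation from 2013 on.
- A reader might set the bias beside the odds ratio of 1.2 for dabigatran that Section 6 reports from the sponsor's previous study. The inverse of 1.2 is 0.83, and only one of the six scenarios, 0.81, reaches it. In all six the bias also works against apixaban, so it would mask excess comparator bleeding and not create it.

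Two further points stand in part. Prior bleeding, HAS-BLED and prior stroke may be partial proxies for treatment history, and the full propensity-score list may be in an analysis plan that is not shown. Neither resolves the conflict in the protocol's own cohort definition.

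**Conclusion.** The conflict between label and rule is certain from the text. As written, continuing users would be reported as initiators. It is also certain that the protocol has no exclusion and no listed covariate for earlier use of the four study drugs, and that Section 8.9 does not draw the consequence.

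That this biases the primary odds ratios is possible but not shown. Both size and direction depend on the shares of continuing users and on their relative bleeding risk, which the documents do not give. The range of 0.98 to 0.81 is illustrative and holds only under the assumed shares and risk ratios. This is a moderate point about definition, adjustment and a missing limitation. It is not a demonstration that the comparison is invalid.

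**What to change.** 1. Replace *initiated* with *received* in Sections 8.1, 8.2 and 8.2.3 and in the abstract, so that conclusions refer to in-hospital users.
2. Add two variables to Table 1 and the propensity score: any study anticoagulant billed at a database hospital in the 12 months before the index admission, and prior hospitalisation with atrial fibrillation. The window must end before admission. The index date is the discharge date, so copying the edoxaban clause would count the index stay itself.
3. Run a sensitivity analysis that excludes patients with such prior billing.
4. State in Section 8.9 that outpatient prior use cannot be seen and that residual prevalent-user bias of unknown direction may remain.

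The cost is one extra query on a baseline period already in the data, some wording, and a small loss of patients in the sensitivity analysis only. The gain from the look-back is limited, because it reaches mainly 2012 stays and stays without an atrial fibrillation code. The relabelling and the stated limitation therefore carry much of the repair.
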